- n. Provide and explain the use of the diary card to the participant (refer to Section 5.19).
- o. Dispense one vaginal ring to each participant and provide vaginal ring use and storage instructions (refer to Sections 5.13 and 6.4).
- p. Instruct the participant to insert the vaginal ring (refer to Section 5.14).
- q. The following procedures are not required, but may be conducted if clinically indicated: physical and pelvic examination, cervicovaginal sample collection for STI testing, provision of treatment and/or referral for STIs and other findings, laboratory testing for safety assessments, urine dipstick analysis (microscopy only if clinically indicated) and cervical sample collection for cytology (if no result is evident within the previous year, or abnormal at last cervical cytology).
- r. Schedule the next visit.

4.3. Trial Visits (Monthly research centre visits for the first one to three months, and 3-monthly research centre visits thereafter)

Note: All visit dates will be calculated from the enrolment visit as baseline date. Each scheduled visit while the participant is on the IP has a window period of \pm 7 days.

- a. Update locator and menses information as necessary.
- b. Obtain and record any AE and concomitant medication information since the last visit.
- c. Record possible social harms (refer to Section 10.2).
- d. Perform urine pregnancy test. Refer pregnant women to local prenatal clinic for support services (refer to Section 5.6).
- e. Provide HIV pre- and post-test counselling (refer to Section 5.3.1).
- f. Perform HIV rapid testing as detailed in Section 5.4.3.

NOTE: Additional procedures for participants who test HIV-positive are also described in Section 5.4.3 of the protocol.

- g. Collect a blood specimen by venepuncture for storage for possible HIV viral genotype resistance and HIV-RNA PCR testing (Blood volume specified in Appendix C).

- h. Collect blood (Blood volume specified in Appendix C) and vaginal fluid samples (refer to Section 5.17) for possible measurement of dapivirine concentrations.

NOTE: *For dapivirine concentration measurements, blood and vaginal fluid samples should preferably be collected prior to removal of the vaginal ring.*

- i. Instruct the participant to remove the vaginal ring. Perform IP accountability and visual inspection of the returned ring(s). Returned rings may be analysed for residual amounts of dapivirine and will be stored until shipment to the analytical laboratory.

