9.2 Primary Endpoint 2 – Adherence

Dapivirine residual levels in used rings will be determined for all participants receiving IP, as a measure of adherence to ring use. The data will be listed, summarised and presented graphically, as described below.

Dapivirine Residual Levels in Used Rings

All used vaginal rings that are returned to the research centres at each trial visit are collected and shipped at regular, pre-defined intervals to an analytical laboratory,

where the rings are analysed to determine the residual amounts of dapivirine in the rings.

For this trial, a reported ring residual level of > 23.5 mg dapivirine will be used as an indication of non-adherence to ring use over the 30-day period (± 7 days) that a woman was to keep the ring *in situ*. Based on the data from the Phase III program, the cut-off value of > 23.5 mg for dapivirine ring residual levels was shown to be a good measure of non-adherence to ring use, indicating no or very little ring use.

The following summaries and graphical presentations will be produced for these data:

- A summary of ring residual levels at each trial visit and at the time of seroconversion, the time of first HIV-1 RNA positive as well as the time of last HIV-1 RNA negative will be presented with standard descriptive statistics – presented overall, by IPM 027 treatment arm, and by research centre. Corresponding box plots will be prepared.
- A descriptive summary of the ring residual levels by trial visit and by category of residual amount (< 20 mg, $20 – 21$ mg, $> 21 – 22$ mg, $> 22 – 23.5$ mg, and > 23.5 mg). This summary will be prepared overall, by IPM 027 treatment arm and by research centre, with corresponding bar charts.
- A summary relating the ring residual levels to time intervals (in days) between consecutive ring replacements (< 23 days, $23 – 37$ days, $> 37 – 84$ days, and > 84 days). Corresponding box plots will be prepared.

Note: All summaries and graphical presentations will be produced for both uncorrected dapivirine ring residual levels (as reported by the analytical laboratory) and residual levels corrected for manufacturing and assay variability, unless otherwise specified.

The aforementioned graphical presentations will be repeated for the ring residuals from the IPM 027 and IPM 032 trials, and will be based only on the participants from IPM 027 who enrolled in IPM 032. However, only the uncorrected ring residual levels will be used.

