9.4.4 Exploratory Endpoint 4: Self-reported acceptability and adherence to vaginal ring use

Consistent with exploratory objective 4, exploratory endpoints 4 and 5 are the proportion of participants who respond positively to questions on ring acceptability at the last product use visit, and participant self-reported patterns of ring use, respectively.

Assessments – Self-reported acceptability

Participant questionnaires will be administered at every trial visit after enrollment, until the last product use visit.

Statistical methods – Self-reported acceptability

The proportion of participants among all trial participants who respond positively (i.e. Yes) to the following two questions at the last product use visit:

- “Do you think it is possible for women to use the ring as requested (i.e. without removing it)?”
- “Do you think women in your community would want to use this ring if it were available?”

A participant will be classified as having found the vaginal ring acceptable if she responds positively to the first question, about keeping the ring inserted as prescribed. Community acceptability will be demonstrated by positive responses to the second question. For each question, the proportion of participants who responded positively,

and the corresponding Fisher's exact 95% confidence interval, will be calculated and presented.

Summary tables with descriptive statistics will be presented for the socio-demographic variables and psycho-social variables collected in the participant questionnaires.

Note: Additional explanatory analyses will utilise the qualitative data from focus group discussions and individual interviews; these analyses will be performed separately from the analyses described in this analysis plan, and will be discussed in the Clinical Study Report.

Assessments – Self-reported adherence

Information on rings dispensed and returned are recorded at each trial visit on the RL CRF. Participant self-reports of accidental ring expulsions and removals are recorded on the EXP CRF.

Statistical methods – Self-reported adherence

Self-reported adherence to the ring regimen will be calculated per visit, and presented descriptively overall and by research centre. The adherence rate per visit will be calculated as:

- $100 \times (\text{number of days that the participant reportedly wore the ring} / \text{the total number of days that the participant was expected to wear the ring})$.

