The number of days that the participant reportedly wore the ring is based on data captured in the Ring Insertion/Removal Log (RL) CRF and the EXP CRF at the scheduled visit and any preceding unscheduled visit between the current and the previous scheduled visit. The total number of days that the participant was expected to wear the ring is a calendar month (30 days) from the insertion date.

The self-reported adherence rates will be presented in the following categories:

- $\geq 90\%$
- $\geq 80\% \text{ to } < 90\%$
- $< 80\%$.

Summary tables with descriptive statistics will be presented for accidental ring expulsions and removals by the participant for reasons other than instructed by the research centre staff.

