Centre Participant ID	Visit Date	IPM 027 Treatment	Date Inserted	Date Removed	Duration of Treatment	Scheduled Duration	Adherence Rate	Adherence Rate Category
Centre XX XXXXXXXXX	ddMMMyyyy	Dapivirine / Placebo	ddMMMyyyy	ddMMMyyyy	XX	XX	XXX	< 80% ≥ 80 to < 90% / ≥ 90%

Adherence rate = 100 x (Duration of Treatment / Scheduled Duration)

Missing or partial dates for when the ring was inserted or removed are treated as missing data during the calculation of the adherence rate

If a participant did not remember/know the date when a ring was expelled or removed, the number of days that the ring was out is counted as one day and applies to the ring that was dispensed during that time

Centre 01: Madibeng Centre for Research (MCR); Centre 02: MatCH Research Unit (MRU); Centre 04: Qhakaza Mbokodo (QM);

Centre 06: MRC/UVRI & LSHTM Uganda Research Unit (MRC/UVRI); Centre 07: Desmond Tutu HIV Foundation (DTHF), Masiphumelele; Centre 08: Ndlovu Care Group (NCG)

Listing 16.2.5.2
Self-Reported Acceptability and Adherence to Investigational Product
Safety Population

Centre Participant ID	Visit Date	Do You Think It Is Possible To Use Ring As Requested (i.e. Without Removing It)?	Do You Think Women In Your Community Would Like To Use This Ring If It Were Available?
Centre XX XXXXXXXX	ddMMMyyyy	Yes / No: XXXXXXXXXXXXXXXX / Don't know / Chose not to answer	Yes / No: XXXXXXXXXXXXXXXX / Chose not to answer

Adherence rate = $100 \times (\text{Duration of Treatment} / \text{Scheduled Duration})$

Missing or partial dates for when the ring was inserted or removed are treated as missing data during the calculation of the adherence rate

If a participant did not remember/know the date when a ring was expelled or removed, the number of days that the ring was out is counted as one day and applies to the ring that was dispensed during that time

Centre 01: Madibeng Centre for Research (MCR); Centre 02: MatCH Research Unit (MRU); Centre 04: Qhakaza Mbokodo (QM);

Centre 06: MRC/UVRI & LSHTM Uganda Research Unit (MRC/UVRI); Centre 07: Desmond Tutu HIV Foundation (DTHF), Masiphumelele; Centre 08: Ndlovu Care Group (NCG)

Listing 16.2.5.3
Returned Ring Log
Safety Population

Centre	Participant ID	Month of Ring Use	Replacement Ring	Shipped for Analysis	Shipped Date	Shared Results with Participant	Results Shared Date
XX	XXXXXXXXXX	XX	Yes / No	Yes / No	ddMMMyyyy	Yes / No	ddMMMyyyy

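### Dividing self-reported ring wear by a fixed 30 days lets visit timing move women between adherence categories

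*SAP*

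**What the plan says.** SAP 9.4.4 (Self-reported adherence, statistical methods) states: "Self-reported adherence to the ring regimen will be calculated per visit". The rate is 100 times days reportedly worn divided by days expected. For the numerator: "The number of days that the participant reportedly wore the ring is based on data captured in the Ring Insertion/Removal Log" and from the expulsion log. For the denominator, the expected time "is a calendar month (30 days) from the insertion date". The section gives no truncation of worn days at 30, no cap at 100% and no adjustment for the interval a ring was actually due to cover. Results go into three groups: at least 90%, 80% to under 90%, and under 80%.

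Table 14.3.5.5 repeats the formula and is laid out by month of ring use, which points to a calculation per ring. Listing 16.2.5.2 divides by a column called Scheduled Duration and does not define it.

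Three other places bear on the interval:
- Protocol 4.3: "Each scheduled visit while the participant is on the IP has a window period of" ± 7 days. Also: "All visit dates will be calculated from the enrolment visit as baseline date".
- Protocol 5.13: in the monthly phase, women are told to take the ring out at the next scheduled visit.
- SAP 9.2, for the objective measure, refers to the "30-day period (± 7 days) that a woman was to keep the ring" in place, and groups replacement intervals of 23 to 37 days together.

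**The concern.** The SAP uses two standards for one interval. For residual drug, a ring changed on day 23 or day 37 is on time. For self-report, the first is a shortfall and the second a surplus. In the monthly phase a woman who comes early within the window and has her ring removed there has followed instructions, yet she loses up to a quarter of her score. A woman seen late gains days that can absorb time with the ring out.

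The error runs in both directions, so it cannot be read as a bias of known sign. The rate is tabulated by centre and by IPM 027 arm, and SAP 6.4 plans to explore differences in adherence across centres. Centres that differ only in how early or late they see women could appear to differ in adherence.

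**Working it through.** **Inputs.** Denominator 30 days (SAP 9.4.4); window ± 7 days (Protocol 4.3); cuts at 80% and 90% (SAP 9.4.4). Ring duration is counted inclusively in Listing 16.2.5.4, as removal date minus insertion date plus 1.

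**Step 1: the plan's own band.** 30 − 7 = 23 and 30 + 7 = 37. This reproduces the 23 to 37 day group in SAP 9.2. The SAP gives no worked adherence value to reproduce.

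**Step 2: the rate as written.** Rate = 100 × worn / 30. For comparison, share of actual interval = 100 × worn / interval.

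| Case | As written | Category | Share of actual interval |
|---|---|---|---|
| 23 days, none out | 23/30 = 76.7% | <80% | 23/23 = 100% |
| 37 days, none out | 37/30 = 123.3% | ≥90% | 37/37 = 100% |
| 37 days, 7 out | 30/30 = 100% | ≥90% | 30/37 = 81.1% |
| 37 days, 10 out | 27/30 = 90.0% | ≥90% | 27/37 = 73.0% |

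**Step 3: how much lateness forgives.** A woman stays in the top category with 27 worn days, so the days out allowed equal the interval minus 27. That is 3 days for a 30-day interval and 10 days for a 37-day interval.

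**Step 4: sensitivity to the day count.** If 23 means elapsed days and the inclusive rule applies, the first case is 24/30 = 80.0%, the middle category. That is still wrong for uninterrupted wear. The last case becomes (38 − 10)/30 = 93.3%, still the top category, against 28/38 = 73.7%.

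Visits are anchored to enrolment, so two consecutive in-window monthly visits can be 30 − 14 = 16 days apart. Uninterrupted wear then scores 16/30 = 53.3%, or 17/30 = 56.7% inclusively. Either way it falls in the lowest category.

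**Step 5: sensitivity to truncation.** Suppose worn days were counted only in the first 30 days. The 37-day unbroken case becomes 30/30 = 100%. With 10 days out, between 3 and 10 of them fall in the first 30 days, so the rate runs from 20/30 = 66.7% to 27/30 = 90.0%. The 23-day case does not change: truncation repairs long intervals in part and short ones not at all.

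**The case against.** The best defence is that a fixed month measures the regimen women are told to follow, which is to keep the ring in for one month. On that view 73.0% is no more correct than 90.0%. This stands in part: the share of the actual interval is a definition, not a truth. But a measure against the instructed regimen should not mark down removal at a permitted visit, nor exceed 100%.

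Second, dividing simply by days from insertion to removal would be worse in one case. A ring lost or taken out for good on day 10 would score 10/10 = 100%, where the present rule gives 10/30 = 33.3%. This stands, and it shapes the fix.

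Third, the examples are window extremes. In the 3-monthly phase two of every three rings are changed at home, not at a visit. So the window bites mainly on the early monthly rings and the ring removed at each 3-monthly visit. This stands; the documents give no frequency.

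Fourth, Table 14.3.5.3 already reports replacement intervals, and Listing 16.2.5.2 shows dates and durations. That makes timing visible but leaves the categories in Table 14.3.5.5 unchanged.

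Three stronger readings are tempting and not supported:
- **That the trial's adherence findings are compromised.** Residual drug is the primary adherence measure, and the non-adherence rule for the per-protocol population in SAP 7.2 uses missed 3-monthly visits, not this rate.
- **That unknown removal dates are always scored favourably**, because "the number of days that the ring was out is counted as one day". The sentence before it in Listing 16.2.5.2 treats missing or partial insertion and removal dates as missing. Protocol 6.5 tells women to put an expelled ring back promptly, so one day can overstate a brief expulsion.
- **That a 3-monthly visit yields about 300%.** The layout of Table 14.3.5.5 by month of ring use suggests one calculation per ring.

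**Conclusion.** The point holds as a stated rule that produces wrong categories, not merely a missing detail. With 23 counted days of wear, a fully compliant woman falls in the lowest category at 76.7%; with 23 elapsed days counted inclusively, she falls in the middle category at 80.0%. Unbroken wear for 37 days gives 123.3%. Ten days out of 37 reaches the top category at 90.0% against 73.0% of the interval.

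The figures assume one calculation per ring and, for the two long-interval results, no truncation at day 30. The SAP states none. How many records would change category cannot be judged from the documents. The consequence is limited to a descriptive, exploratory endpoint, but the correction is cheap and should be made.

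**What to change.** Amend SAP 9.4.4 so that, for each ring:
- **Denominator:** days from insertion to the visit at which the ring was removed as instructed, or to insertion of the next ring. It never ends at an unscheduled removal, expulsion or loss.
- **Numerator:** those same days minus days out.
- **Day count:** the same convention in both.

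The rate then cannot exceed 100%. The 23-day case scores 23/23 = 100% and the 37-day case with 10 days out scores 27/37 = 73.0%. A ring lost on day 10, with the next inserted on day 30 (an assumed date), scores 10/30 = 33.3%, so early loss still counts as non-wear. The SAP should also say what happens to a last ring with neither end point, for example after loss to follow-up.

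Define Scheduled Duration in Listing 16.2.5.2 and the footnote of Table 14.3.5.5 to match. Late replacement no longer shows in the rate: a ring left in well past its month scores 100%. Cross-refer to Table 14.3.5.3, which already groups intervals as under 23, 23 to 37, over 37 to 84, and over 84 days.

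The cost is SAP wording and one reprogrammed derivation; insertion and removal dates are already on the ring log CRF. The downside is that rates are no longer expressed against a fixed 30 days.

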10 EVALUATION OF SAFETY PARAMETERS

10.1 Adverse Events

An AE is defined as any untoward medical occurrence in a clinical trial participant. An AE can therefore be any unfavourable and unintended sign (including an abnormal

laboratory assessment finding), symptom or disease temporally associated with the participation in this trial, whether or not considered related to the IP. All AEs will be coded using MedDRA (Version 19.0).

10.1.1 Treatment Emergent Adverse Events (TEAEs)

TEAEs are defined as AEs which occurred/worsened after the first insertion of the IP, up to six weeks after last ring use.

10.1.2 Product-related Adverse Events

Product-relatedness is reported as “Related” or “Not Related”. While every effort is made to ensure that this field is not missing through data reviews and queries, if the relationship with the IP is missing on the CRF, it will be assumed that the AE was “Related” to the IP.

Summary Tables

A summary table of TEAEs will be presented, indicating the frequency and proportion of participants with:

- At least one TEAE
- At least one serious TEAE
- At least one Division of Acquired Immunodeficiency Syndrome (DAIDS) Grade 3 or 4 TEAE
- At least one product-related TEAE
- At least one serious product-related TEAE
- A TEAE leading to death
- A TEAE leading to premature (permanent) IP discontinuation
- A TEAE leading to temporary IP discontinuation
- A TEAE leading to trial discontinuation.

If meaningful, the same summary tables may be produced for non-TEAEs.

The definitions and location of data elements to be used to define each measure are described in Table 2 below.

Table 2 Definition and Data Sources of AEs

Measure	Statistic	Data Sources*
Participants with at least one TEAE	Frequency	A participant reported with an AE in the AE CRF Source: AE
Participants with at least one serious TEAE	Frequency	A participant reported as having an SAE per the AE CRF Source: AE

Measure	Statistic	Data Sources*
Participants with at least one DAIDS Grade 3 or 4 TEAE	Frequency	A participant reported as having a DAIDS Grade 3 or 4 AE Source: AE
Participants with at least one product-related TEAE	Frequency	A participant reported as having a “related” event, per the AE CRF Source: AE
Participants with at least one serious product-related TEAE	Frequency	A participant reported as having a “related” SAE, per the AE CRF Source: AE
Participants with a TEAE leading to death	Frequency	A participant reported as having an AE with the reported outcome “fatal” per the AE CRF Source: AE
Participants with a TEAE leading to premature (permanent) IP discontinuation	Frequency	A participant reported as having an AE with an action taken of “drug withdrawn” per the AE CRF Source: AE
Participants with a TEAE leading to temporary IP discontinuation	Frequency	A participant reported as having an AE with an action taken of “drug interrupted” per the AE CRF Source: AE
Participants with a TEAE leading to trial discontinuation	Frequency	A participant reported as having a Trial Completion status of “Participant discontinued from the trial early” and a reason of “Adverse event/intercurrent illness” per the TC CRF Source: TC

* Percentages will use the total number of enrolled participants as denominator.

A by-participant listing of all TEAEs will include the variables in Table 3 below.

Table 3 AE Variables

Variable	Data Type	Data Sources
SAE	Dichotomous	Yes/No Source: AE
Outcome	Nominal	Fatal, Not recovered/not resolved, Recovering/resolving, Resolved/recovered w/sequelae, Recovered/resolved, Unknown Source: AE
Severity	Ordinal	Grade 1 Mild, Grade 2 Moderate, Grade 3 Severe, Grade 4 Potentially life-threatening, Grade 5 Death Source: AE
Relationship	Ordinal	Related, Not related Source: AE
Action	Nominal, DDMMYY	Dose not changed, Drug interrupted, Drug withdrawn, N/A Date interrupted, date reintroduced, date withdrawn

Variable	Data Type	Data Sources
		Source: AE
Other action	Nominal	None, Treatment medication, Non-drug therapy, Other Source: AE
SOC	Nominal	System Organ Class Source: AE
PT	Nominal	Preferred Term Source: AE
AE Term (Verbatim)	Nominal	Reported Event Source: AE

The incidence of TEAEs will be presented by SOC and PT, overall, IPM 027 treatment arm and by research centre.

The incidence of the following TEAEs by severity will be presented by SOC and PT, overall, IPM 027 treatment arm and by research centre:

- TEAEs
- Serious TEAEs
- Product-related TEAEs
- Serious product-related TEAEs
- Social harms reported as TEAEs (refer to Section 10.9).

In addition, for IPM 027 participants who directly enrolled in the IPM 032 trial from the open-label treatment period of IPM 027, a subgroup display of Overall TEAEs, TEAEs by worst severity and Product-related TEAEs will be presented.

Maximum severity will be assumed for an AE with missing severity.

A by-participant listing of all deaths, SAEs, non-TEAEs, permanent IP discontinuations and premature trial discontinuations will be presented in Appendix 16 of the CSR. These by-participant listings will include variables described in the summary of TEAEs in addition to the following variables:

Table 4 Additional AE Variables

Variable	Data Type	Data Sources
AE start date	DDMMYY	Start date Source: AE
Outcome date	DDMMYY	Outcome date Source: AE
Trial day	Continuous	Trial day = (Start Date of AE – Date of First Use of IP) + 1 Source: Calculated from AE (AESTDAT) and ENR

Variable	Data Type	Data Sources
		(TCDAT)
Duration (days)	Continuous	
Duration (days) = $AEENDAT - AESTDAT + 1$
 
Source: Calculated from AE
 
Duration will only be calculated if both the start and stop dates are available, or if the start date is known and the AE is ongoing at trial end; in such cases, the duration will be reported as "> (Trial Termination Date – Start Date of AE) + 1"

